5.2. Protocol Deviations

All protocol deviations will be entered and tracked within the PPD Clinical Trial Management System (CTMS) by the study team throughout the conduct of the study in accordance with PPD's Study Deviation Rules Document. A significant deviation is any deviation that may affect primary efficacy and safety assessments (as applicable), the safety or mental integrity of a

subject, or the scientific value of the trial. A significant deviation does not necessarily affect the primary endpoint and be excluded from the PP set.

Data will be reviewed by the study team prior to unblinding and official database lock for final analysis at Day 43 to ensure all significant deviations are captured and properly categorized. Particularly, a final list of significant protocol deviations leading to exclusion from the PP set (also referred to as major protocol deviations) will also be determined by the study team and flagged in the final CTMS deviation data file.

Major protocol deviations are defined as significant deviations that might directly or indirectly impact the primary efficacy endpoint (time to fecal viral RNA clearance) and may include (but are not limited to) the following:

- Did not meet the key inclusion or exclusion criteria
- Had poor compliance with study treatment (< 80%)
- Received prohibited concomitant medications through the Day 43 follow-up visit
- Had a randomization error
- Received incorrect study drug

Significant protocol deviations will be summarized by treatment group and overall. A listing will also be provided for significant protocol deviations with a flag indicating major protocol deviations. Non-significant protocol deviations will be just listed. Summaries will be conducted on all subjects that were randomized.

6. Demographics and Baseline Characteristics

All summaries will be based on the safety set and presented separately for Part 1 and Part 2 of the study.

6.1. Demographics

A summary of demographics and baseline information will be presented by treatment group and overall. The demographic characteristics consist of age, sex, race, and ethnicity. The baseline characteristics consist of the WHO severity score as reported in [Appendix 16.2](#), loose or watery stool on Day 1, abdominal symptom(s) on Day 1, stool test for SARS-CoV-2 by RT-qPCR on Day 1, stool test for bacteria or parasites at Screening (local laboratory) and COVID-19 vaccination(s) prior to Screening.

Age (years) will be summarized using descriptive statistics. The number and percentage of subjects will be presented for each of the following variables and its associated categories:

- Age (<65, ≥65)
- Sex (Male, Female)
- Race (White, African American, Asian, American Indian or Alaska Native, Native Hawaiian or Other Pacific Islander, Other),
- Ethnicity (Hispanic or Latino, Not Hispanic or Latino),
- WHO severity score (ordinal categorical scores of 1 to 7)

- Loose or watery stool on Day 1 (Yes, No) as collected on the Diarrhea Clinical Assessment at Randomization eCRF
- Abdominal symptom(s) on Day 1 (Yes, No)
- Stool test for SARS-CoV-2 by RT-qPCR on Day 1 (Positive, Negative)
- Stool test for bacteria or parasites at Screening (Positive, Negative)
- COVID-19 vaccination(s) prior to Screening (Yes, No)

Subject demographic and baseline characteristics will also be presented in a listing.

6.2. Medical History

6.2.1. General Medical History

Medical history will be coded using the Medical Dictionary for Regulatory Activities (MedDRA) Version 24.0. The number and percentage of subjects with any medical history will be summarized overall and for each system organ class and preferred term by treatment group and overall. Percentages will be calculated based on number of subjects in the safety set.

Subject medical history data including specific details, will also be presented in a listing.

7. Treatments and Medications

All summaries will be based on the safety set and presented separately for Part 1 and Part 2 of the study.

7.1. Prior and Concomitant Medications

All medications taken during the study, from screening visit to short-term follow-up (Day 43), will be collected. All medications will be coded according to the World Health Organization (WHO) drug dictionary (WHODrug Global B3 2021 MAR or higher version). Details for imputing missing or partial start and/or stop dates of medications are described in [Appendix 16.3](#).

A prior medication is defined as any medication with a start date prior to the first dose of study drug. A concomitant medication is defined as any medication that has a start date that is on or after the first dose of study drug or any medication with a start date prior to the first dose and a stop date after the first dose of study drug. Furthermore, a medication could be labeled as both a prior and concomitant medication if it was started prior to the first dose of study drug and continued after the first dose of study drug.

The number and percentages of subjects with at least one prior medication will be summarized by treatment group and overall. The number and percentages of all prior medications will be summarized by treatment group and overall and listed by Anatomical Therapeutic Chemical (ATC) level 2 and preferred term.

The number and percentages of subjects with at least one concomitant medication will be summarized by treatment group and overall. The number and percentages of all concomitant

medications will be summarized by treatment group and overall and listed by Anatomical Therapeutic Chemical (ATC) level 2 and preferred term.

Prior and concomitant medications, including prohibited medication, will also be presented in a listing.

7.2. Study Treatments

7.2.1. Extent of Exposure

Duration of study drug in days will be calculated as: last dose date – first dose date + 1 day, regardless of study drug interruption (i.e., missed dose). Study drug exposure will be summarized by treatment group and overall using the safety set.

A summary of each subject's exposure will also be presented in a listing.

7.2.2. Treatment Compliance

The study drug compliance will be calculated as: $100 * [1 - (\text{total number of days with any missed dose} / \text{duration of study drug in days})]$. Days of missed dose (full or partial dose) will be based on the Missed Dose eCRF.

Study drug compliance will be summarized for all subjects in the safety set with descriptive statistics by treatment group and overall. Additionally, the number and percentages of subjects in each compliance category (<80% and ≥80%) will be also presented by treatment group and overall.

A summary of each subject's compliance will also be presented in a listing.

8. Efficacy Analysis

Primary and secondary efficacy analyses will be conducted on efficacy data collected through the Day 43 follow-up visit for all randomized subjects and will be included as part of the Day 43 Final Analysis for the main clinical study report (CSR).

All efficacy analyses will be performed using the FAS or EE set and will be presented separately for Part 1 and Part 2 of the study unless otherwise specified. For Part 1, due to the small sample, only descriptive summary statistics will be provided by treatment group and no inferential statistical tests will be performed. For Part 2, all efficacy data will be summarized descriptively and also analyzed using appropriate inferential statistical tests as applicable. Relevant subject data listings will also be provided to support all efficacy analyses and will be presented separately for Part 1 and Part 2 of the study unless otherwise specified.

Missing data will not be imputed.

8.1. Primary Efficacy Endpoint

The primary endpoint for Part 2 of the study is the time to fecal viral RNA clearance for subjects with a positive stool test for SARS-CoV-2 on Day 1 assessed by RT-qPCR in the niclosamide arm compared to the placebo arm.

Time to fecal viral RNA clearance is defined as the time (days) from the first dose of study treatment to the first stool RT-qPCR sample negative for SARS-CoV-2, after which all stool samples (if any) are negative. A stool sample is considered negative for SARS-CoV-2 if the test result is reported as “Not Detected”; otherwise, the stool sample is positive if the test result is reported as “Detected”. Furthermore, an “Inconclusive” test result is considered positive if it is followed directly by a positive test result; an “Inconclusive” test result is considered negative if it is followed directly by a negative test result. Subjects without fecal viral RNA clearance will be censored as follows:

- In the case of death of any cause, the subject will be considered to have the worst outcome with censoring at the planned Day 43 follow-up visit.
- In the case of hospitalization for any reason and withdrawal of consent, the subject will be considered to have the worse outcome with censoring at the planned Day 43 follow-up visit.
- In the case of study discontinuation prior to Day 43 follow-up visit due to any other reasons, the subject will be censored at the last available visit.
- In the case of study completion for Day 43, the subject will be censored at the date of the actual Day 43 follow-up visit.

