4.3.2. Efficacy Evaluable (EE) Set

The efficacy evaluable (EE) set will consist of all randomized subjects who received at least one dose of study drug, had a positive stool test for SARS-CoV-2 on Day 1 assessed by RT-PCR, and did not test positive for bacteria or parasites in the screening stool analysis by the local laboratory. The EE set will be used for the primary efficacy endpoint and relevant gastrointestinal efficacy secondary endpoints and will be analyzed according to the study treatment as randomized.

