8.1.1. Primary Analysis

The analysis of the primary efficacy endpoint, time to fecal viral RNA clearance, will be conducted on the EE set.

The number and percentages of subjects achieving and not achieving the first fecal viral RNA clearance will be summarized up to each post-first dose study visit (Days 4, 8, 15, 22, 29, 36, and 43) by treatment group. For each study visit, only subjects with available assessment at the visit or having a negative stool test before the visit will be included in the summary and counted in the denominator for the percentages.

A stratified log-rank test will be used to compare time to fecal viral RNA clearance between niclosamide and placebo treatment groups adjusting for stratification factors, age (<65 years or ≥65 years) and sex (female or male). The two-sided p-value will be reported. The estimate of the hazard ratio (niclosamide vs. placebo) and the associated 95% confidence interval (CI) will be obtained from a Cox Proportional Hazards model adjusting for stratification factors and will also be reported.

Kaplan-Meier curves with 95% CIs will be generated for the total population by treatment group. Summary statistics obtained from Kaplan-Meier estimates, including the median time to fecal viral clearance with corresponding 95% CI and the proportion of subjects achieving fecal viral clearance at 3, 7, 14, 21, 28, 35, and 42 days post first dose (Day 1), will be summarized by treatment group.

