8.2.5. Time from first dose of study treatment to improvement of abdominal symptoms

Only subjects with abdominal symptom(s) on Day 1 will be included in this analysis.

The overall severity of abdominal symptoms and the date of assessment will be collected on the Diarrhea Clinical Assessment. A summary table of severity will include the number of subjects with an assessment available and the number and percentage of subjects within each severity category at each study visit (Baseline, Days 4, 8, 15, 22, 29, 36, and 43) by treatment group. The proportion of subjects with any improvement from baseline of abdominal symptoms will also be provided in the summary table by treatment group. Improvement of abdominal symptoms is defined as any severity reduction from baseline by at least one level (i.e., mild to normal, moderate to mild or normal, or severe to moderate or mild or normal).

Time to the first improvement of abdominal symptoms is defined as the time in days from the first dose of study treatment to the first improvement of abdominal symptoms. Subjects without improvement of abdominal symptoms will be censored using the same rules as described for the primary efficacy endpoint in [Section 8.1](#). Time to improvement of abdominal symptoms will be analyzed using the same time to event methods as described for the analysis of the primary endpoint in [Section 8.1.1](#).

8.2.6. Proportion of subjects with a negative stool test for SARS-CoV-2 on Day 1 who acquire SARS-CoV-2 in stool through Day 43

This analysis will be conducted on the FAS and include only all subjects with a negative stool test for SARS-CoV-2 on Day 1.

A summary table will include the number and percentage (proportion) of subjects acquiring SARS-CoV-2 by treatment group first overall after Day 1 through Day 43 visit, then for each post-first dose study visit (Days 4, 8, 15, 22, 29, 36, and 43). For each study visit, only subjects with available assessment at the visit or having a positive stool test before the visit will be included in the summary and counted in the denominator for the percentages.

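### The rule for Inconclusive stool results is not limited to post-dose samples, so a Day 1 Inconclusive can enter or leave the primary analysis set on an on-treatment result; the numerical effect is small.

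*SAP*

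**What the plan says.** SAP 8.1 classifies stool samples in general terms: "A stool sample is considered negative for SARS-CoV-2 if the test result is reported as" Not Detected, and positive if reported as Detected. For the third category, an Inconclusive "test result is considered positive if it is followed directly by a positive test result"; likewise it "test result is considered negative if it is followed directly by a negative test result". Neither branch mentions baseline or follow-up. The same section restricts the primary endpoint to subjects with a positive Day 1 stool test.

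SAP 4.3.2 admits to the EE set a subject who "had a positive stool test for SARS-CoV-2 on Day 1 assessed by RT-PCR" and gives no separate rule for an Inconclusive on that day. It states that "The EE set will be used for the primary efficacy endpoint", and SAP 8.1.1 confirms that the analysis of "time to fecal viral RNA clearance, will be conducted on the EE set". SAP 8.2.6, the acquisition endpoint, will "include only all subjects with a negative stool test for SARS-CoV-2 on Day 1".

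Protocol 10.2 lists the Day 1 stool sample under pre-dose procedures. The next scheduled sample is Day 4 (±1 day), during treatment (Protocol 10.4). Protocol 12.4 defines a negative through the limit of quantification and has no Inconclusive category.

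**The concern.** A baseline characteristic that decides who is analysed should be fixed before treatment can affect it. If the 8.1 rule is applied to Day 1, it is not. A patient with an Inconclusive Day 1 result who is negative on Day 4 becomes Day 1 negative and leaves the EE set. The same patient, still positive on Day 4, becomes Day 1 positive and enters it. If niclosamide speeds clearance, more such patients leave from the active arm. Those who do enter this way cannot have cleared at the first visit.

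The planned checks would not show this. The only sensitivity analysis of the primary endpoint (SAP 8.1.2) uses the PP set, which is a subset of EE and inherits the same selection.

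The rule also leaves gaps. An Inconclusive followed by another Inconclusive, or by no further sample, has no clear classification.

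**Working it through.** **Inputs from the plan (SAP 4.1).** Exponential clearance; medians 10 days (niclosamide) and 21 days (placebo), so hazard ratio 21/10 = 2.1; 30 stool-positive patients per arm; two-sided log-rank test; assessments at 3, 7, 14, 28 and 42 days after first dose; stated power 74% at alpha 0.05 and 83% at 0.10.

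**The plan's own figure.** Simulation with these inputs (6,000 runs, unstratified test) gives 73.8% and 83.3%. As a cross-check, expected events by day 42 are 30 × (1 − 2^(−42/10)) + 30 × (1 − 2^(−42/21)) = 28.37 + 22.50 = 50.87. Schoenfeld power, Φ(√(E/4) × ln 2.1 − 1.960), is 75.4% at alpha 0.05, and 84.2% at alpha 0.10 with 1.645 in place of 1.960. The stated figures reproduce.

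**Chance of removal.** Take a truly positive patient with an Inconclusive Day 1 result. Under the rule as written, removal means clearing by the first post-dose sample, with probability 1 − 2^(−d/median).

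| Days after first dose (d) | Niclosamide | Placebo |
|---|---|---|
| 2 | 12.9% | 6.4% |
| 3 (Day 4 visit) | 18.8% | 9.4% |
| 4 | 24.2% | 12.4% |

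The ratio is about 2:1 across the visit window. If these patients have low viral load and clear at three times the hazard (an assumption), removal by day 3 is 1 − 2^(−9/10) = 46.4% and 1 − 2^(−9/21) = 25.7%.

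**Effect on the analysis.** The Inconclusive rate q is assumed. Simulation used visits at 3, 7, 14, 21, 28, 35 and 42 days, 5,000 runs per cell, an unstratified log-rank test, and all Inconclusives truly positive with the same hazard as other patients.

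| q | Mean EE size, niclosamide / placebo | Power: rule as written | Power: all counted positive | Power: all excluded | Type I error: rule as written |
|---|---|---|---|---|---|
| 5% | 29.7 / 29.9 | 74.1% | 74.9% | 72.3% | 5.3% |
| 10% | 29.4 / 29.7 | 72.5% | 75.2% | 69.3% | 5.2% |
| 20% | 28.9 / 29.4 | 74.1% | 74.0% | 65.2% | 4.9% |
| 30% | 28.3 / 29.2 | 71.7% | 73.6% | 58.1% | 5.3% |

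Simulation noise is visible: at q = 0 the three rules are identical, yet their runs gave 73.5%, 75.1% and 74.6%. The one-step hazard ratio averaged 2.37 to 2.40 under the rule as written and 2.37 to 2.39 with all counted positive. It sits above 2.1 because clearance times are grouped by visit, so only the comparison between rules matters.

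**Why the hazard ratio barely moves.** The rule alters only the first visit; later risk sets are unchanged. With p the clearance probability by day 3, the first-visit event fraction becomes (1 − q)p / (1 − qp). At q = 20% this is 0.8 × 0.1877 / (1 − 0.2 × 0.1877) = 0.156 on niclosamide and 0.8 × 0.0943 / (1 − 0.2 × 0.0943) = 0.0769 on placebo. Their ratio is 2.03, against 0.1877 / 0.0943 = 1.99 without the rule. What is lost is events: 0.2 × 30 × (0.1877 + 0.0943) = 1.69 of 50.87. Schoenfeld power falls from 75.36% to 73.94%, about 1.4 points.

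**Faster-clearing scenario.** At three times the hazard, the mean number removed (placebo / niclosamide) is 0.76 / 1.40 at q = 10% and 1.54 / 2.76 at q = 20%. The power difference from counting all as positive remains within about 3 points. Here excluding all Inconclusives gives almost the same power as the rule as written: 73.0% against 73.2%, 69.2% against 69.8%, and 65.2% against 65.4% at q = 5%, 10% and 20%.

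**Acquisition endpoint (SAP 8.2.6).** A Day 1 Inconclusive who is positive on Day 4 is read as Day 1 positive, leaves the denominator and cannot count as acquired. One who is negative on Day 4 stays in. Such patients therefore cannot acquire by Day 4, by construction.

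**The case against.** The best defence is that the rule sits inside the definition of time to clearance and was meant for follow-up samples. Intent supports this. Protocol 5.2 has stool screened just before treatment and places the primary analysis in patients positive at enrollment; Protocol 9.4 speaks of the pre-treatment sample; SAP section 4 defines baseline as no later than the date of first dose. On that reading a Day 1 Inconclusive is simply not a confirmed positive. But SAP 8.1 does not state the limit, and if it applies, the SAP has no rule at all for a Day 1 Inconclusive and the choice falls to programming. Either reading needs the same clarification.

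A reader might infer that SAP 6.1, which tabulates Day 1 stool status as positive or negative only, forces every Inconclusive through the rule. It does not. SAP section 4 allows a Missing row where the table shells specify one, and a baseline table does not define an analysis set.

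It is also fair that the calculations treat every Inconclusive as truly positive. For a patient who was truly negative on Day 1, exclusion after a negative Day 4 sample is correct.

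**Conclusion.** The point stands as a defect of specification. As written, membership of the primary analysis set, and of the 8.2.6 denominator, can depend on an on-treatment result. Removal of truly positive Day 1 Inconclusives would be about 19% on niclosamide and 9% on placebo under the plan's medians.

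Three stronger readings are not supported. Type I error is not inflated: with identical arms, removal is equal and the simulated error is 4.9% to 5.3%. Dilution of the hazard ratio is not shown; the estimates agree within simulation noise. A claim that 8.2.6 understates new stool positivity does not follow either. Someone Inconclusive on Day 1 and positive on Day 4 may already have been shedding, so the direction depends on an unknown true status. SAP 8.2.6 also specifies only counts and percentages.

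The size, about 0 to 3 points of power, rests on assumed Inconclusive rates of 5% to 20%, exponential clearance at the plan's medians, and an unstratified test, since the documents give no stratum sizes. The case for change is one of principle and low cost.

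**What to change.** In SAP 8.1, state that the look-ahead rule applies to post-dose samples only. In SAP 4.3.2 and 8.2.6, state that Day 1 status is classified from pre-dose information alone, by one rule fixed before unblinding and applied alike in both arms; a re-test of the pre-dose sample is one option. Run the primary analysis both ways, with Day 1 Inconclusives counted as positive and with them excluded, and name one as primary in advance.

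The drafting cost is a few sentences and one additional run. The statistical cost depends on the choice. If the Inconclusives are truly positive and clear at the same rate as other patients, excluding them all leaves power of about 72%, 69% and 65% at rates of 5%, 10% and 20%, against about 74% to 75% if they are counted as positive. Counting them as positive may admit some patients who were truly negative on Day 1.

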9.4 Study Population

Both Parts:

Eligible patients will have a diagnosis of COVID-19 with or without respiratory symptoms. No gender and/or ethnicity restrictions will apply. Each patient should meet all the inclusion and none of the exclusion criteria in order to be eligible for the study.

Part 1:

The study population will include 1 or 2 cohorts of approximately 9 patients (up to approximately 18 patients) randomized in a ratio of 2 active to 1 placebo. Patients will have a primary diagnosis of COVID-19. Patients may be hospitalized, inpatient in a research unit, or seen in an outpatient clinic or in a home care setting. At-home assessments may be performed using a combination of remote digital monitoring of patient-reported information, home visits by qualified research team staff (include nurses or medical assistants), and telehealth evaluation by study investigators. Implementation of the home-based outpatient assessment, including remote digital monitoring and telehealth evaluation, may include use of a digital application.

Part 2:

Part 2 will enroll up to approximately 150 patients receiving at least one dose of study treatment. Patients may be hospitalized, inpatient in a research unit, or seen in an outpatient clinic or in a home care setting.

If a patient begins treatment but is not confirmed to have a positive SARS-CoV-2 result from the pre-treatment stool sample by the central lab, the patient will remain on randomized treatment and will continue study assessments.

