12.8 Handling of Missing Data

All reasonable efforts will be made to reduce the rate of missing data. Investigators will be trained about the importance of patient retention and full data capture. In addition, reasonable attempts should be made by the investigators to emphasize continued subject's participation for the full duration of the trial.

Missing data for the primary endpoint will be handled as follows:

1. In the case of death of any cause, the patient will be considered to have the worst outcome with censoring at the planned follow-up visit (Day 43).
2. In the case of patients who are hospitalized for any reason and withdraw consent, the patient will be considered to have the worst outcome with censoring at the planned follow-up visit (Day 43).
3. In the case of loss to follow-up or other reasons unrelated to COVID-19 for discontinuing the study, the data will be considered missing at random and will be censored at the last available visit if the patient does not have fecal viral RNA clearance before discontinuation from the study.

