8.1.2. Sensitivity Analysis

The analysis of the primary efficacy endpoint, time to fecal viral RNA clearance assessed by RT-qPCR, will also be conducted on the PP set.

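### SAP 8.1 censors COVID-19-related study exits at the last visit, past the limit set in protocol 12.8, without declaring the change or testing its effect

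*SAP*

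**What the plan says.** Protocol 12.8 has three rules for missing primary-endpoint data.

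1. Death from any cause: worst outcome, censored at planned Day 43.
2. Hospitalization with withdrawal: "In the case of patients who are hospitalized for any reason and withdraw consent, the patient will be considered to have the worst outcome", again censored at Day 43.
3. Loss to follow-up, and "other reasons unrelated to COVID-19 for discontinuing the study, the data will be considered missing at random": censored at the last available visit if clearance has not occurred.

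SAP 8.1 keeps the first two. Its rule for deaths reads: "In the case of death of any cause, the subject will be considered to have the worst outcome with censoring at the planned Day 43". Its rule for hospitalized withdrawals reads: "In the case of hospitalization for any reason and withdrawal of consent, the subject will be considered to have the worse outcome". Its third rule applies to discontinuation before the Day 43 visit "due to any other reasons, the subject will be censored at the last available visit". The requirement that the reason be unrelated to COVID-19 is gone.

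SAP Section 1 says the plan is based on protocol Section 12. SAP Section 14 lists the Bristol scale change, the 0.5-day imputation and the absence of censoring for last watery stool, but not this change. SAP 8.1.2 plans one sensitivity analysis: the primary analysis "will also be conducted on the PP set". That changes the patients analysed and leaves the censoring rule as it is.

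**The concern.** The stratified log-rank test, the Cox model and the Kaplan-Meier estimates in SAP 8.1.1 all take censoring to be unrelated to the time at which the patient would have cleared. The protocol accepts this for exits unrelated to COVID-19 and, by its wording, not for the others.

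The others can occur. Under protocol 9.4, "Patients may be hospitalized, inpatient in a research unit, or seen in an outpatient clinic or in a home care setting", so a patient can worsen and leave without being admitted. A hospitalized patient who leaves for a reason other than withdrawing consent also falls under the SAP's third rule. If such patients clear slowly, last-visit censoring credits them with the clearance rate of those who stay.

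The same censoring rules are reused for first formed stool (SAP 8.2.2), abdominal symptoms (8.2.5), WHO-score improvement (8.3.1) and nasopharyngeal clearance (8.3.6). For WHO-score improvement, leaving because of worsening bears directly on the endpoint.

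**Working it through.** **Where each exit without clearance falls**

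| Exit | Protocol 12.8 | SAP 8.1 |
|---|---|---|
| Death | Worst outcome, Day 43 | Same |
| Hospitalized and withdraws consent | Worst outcome, Day 43 | Same |
| Loss to follow-up | Last visit | Same |
| Other reason, unrelated to COVID-19 | Last visit | Same |
| Other reason, related to COVID-19 | No rule stated | Last visit |

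Only the last row differs.

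**Inputs from the documents.** Exponential clearance with medians of 10 days (niclosamide) and 21 days (placebo), 30 stool-positive patients per arm, two-sided alpha 0.05 (SAP 4 and 4.1). Stool visits at 3, 7, 14, 21, 28, 35 and 42 days after first dose (SAP 8.1.1). No dropout allowance is stated: 150 × 0.40 = 60 exactly.

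**The plan's own figure.** Simulating 40,000 trials with assessments at Days 3, 7, 14, 28 and 42 and an unstratified log-rank test gives 73.5% power at alpha 0.05 and 83.3% at 0.10, against the stated 74% and 83%. As a cross-check, expected events are 30 × [(1 − 2^(−4.2)) + (1 − 2^(−2))] = 30 × (0.9456 + 0.75) = 50.9. The Schoenfeld formula with hazard ratio 2.1 gives z = √(50.9/4) × ln 2.1 − 1.96 = 0.69, or 75.4%. The model reproduces the plan.

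**Day-42 clearance under the two rules.** Assumptions: a fraction p of the arm leaves for COVID-19-related reasons, none of them would have cleared by Day 42, and each is censored at one of the first six visits with equal probability. For visit j at time t(j), with t(0) = 0 and median m:

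- at risk: n(j) = (1 − p)·2^(−t(j−1)/m) + p·(7 − j)/6
- events: d(j) = (1 − p)·[2^(−t(j−1)/m) − 2^(−t(j)/m)]
- last-visit censoring: 1 − Π[1 − d(j)/n(j)]
- worst outcome: (1 − p)·(1 − 2^(−42/m))

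For placebo with p = 0.10, n(1) = 1.0 and d(1) = 0.0848, so 0.9152 remain uncleared. The product continues 0.8125, 0.6592, 0.5342, 0.4316, 0.3465, 0.2750. Last-visit clearance is 72.5%; worst outcome is 0.90 × 0.75 = 67.5%.

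| Arm, fraction leaving | Last visit | Worst outcome | Difference (points) |
|---|---|---|---|
| Niclosamide, 5% | 93.5% | 89.8% | 3.7 |
| Placebo, 10% | 72.5% | 67.5% | 5.0 |
| Placebo, 15% | 71.1% | 63.75% | 7.4 |

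Across 5% to 15% in either arm, the same formulas run from 2.5 points (placebo, 5%) to 10.6 points (niclosamide, 15%).

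**Between-arm difference.** With 5% leaving niclosamide and 10% leaving placebo, it is 93.5 − 72.5 = 21.0 points under last-visit censoring and 89.8 − 67.5 = 22.3 under worst outcome. With 10% leaving niclosamide only, it is 92.3 − 75.0 = 17.3 against 85.1 − 75.0 = 10.1. The SAP rule shrinks the difference in the first case and enlarges it in the second.

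**Log-rank test, 30 per arm, leavers never clearing.** Pattern A has leaving times uniform over days 0 to 21. Pattern B has leaving at a random one of the first six visits.

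| Scenario (niclosamide/placebo leaving) | Last visit | Worst outcome |
|---|---|---|
| Power, 5%/5%, A | 72% | 63% |
| Power, 5%/5%, B | 70% | 63% |
| Power, 10%/10%, A | 69% | 53% |
| Power, 10%/10%, B | 64% | 53% |
| Power, 10%/0%, A | 66% | 33% |
| Power, 0%/10%, A | 77% | 88% |
| Medians 21 vs 21, 0%/10%: result favours niclosamide, A | 3.4% | 8.9% |
| Same, B | 4.8% | 8.6% |
| Medians 21 vs 21, 10%/0%: result favours niclosamide, A | 1.9% | 0.5% |

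The nominal value in the last three rows is 2.5%. With equal leaving rates it stays near 2.5% under both rules. Ten percent of an arm is three patients.

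**The case against.** The strongest reply is that no protocol rule is overturned. Protocol 12.8 assigns worst outcome to two cases only, and the SAP keeps both. For the remaining COVID-19-related exits the protocol is silent and the SAP fills the gap. That stands. A reader might infer that the protocol requires worst-outcome handling for these exits. It does not: it limits the missing-at-random rule and stops there.

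The affected group may also be small. Protocol 10.8.1 keeps patients who stop study drug in follow-up, and 9.7.6 lets those who interrupt dosing because of progression resume. Visits can take place at home. Only departure from the study counts, and the documents give no rate for it. This limits the likely size but does not remove the gap.

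A reader might also infer that the SAP rule favours niclosamide. The calculations do not support that: the direction depends on which arm loses more such patients.

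Finally, worst outcome is not a neutral correction. With equal clearance among those who stay and more exits on placebo, it raises the chance of a favourable result to nearly 9%, because it partly tests the difference in leaving. Whether that counts as treatment effect is a question about the estimand. This stands too, and is a reason to report both rules instead of replacing one with the other.

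**Conclusion.** The point holds in a limited form. SAP 8.1 carries last-visit censoring of the primary endpoint beyond the condition in protocol 12.8, does not declare this, and plans no analysis that would show whether it matters. The text alone establishes that.

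The size rests on assumed leaving rates and on leavers being non-clearers. In the three clearance scenarios tabulated, Day-42 clearance is overstated by about 4 to 7 points in the arm concerned. The between-arm effect has no fixed direction, and type I error stays near nominal when exits are equal. It would be wrong to conclude that the primary test is invalid or that worst outcome must become the primary rule.

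**What to change.** Before unblinding:

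1. Reconcile the third censoring bullet in SAP 8.1 with protocol 12.8. Restore the condition on COVID-19-unrelated reasons and state a rule for the remaining exits, or keep the wider rule with a justification. Record any departure in SAP Section 14.
2. Classify each study discontinuation, blinded, as COVID-19-related or not. SAP 5.1 summarizes discontinuation reasons, but neither document shows this category, and a recorded consent withdrawal would not reveal it.
3. Pre-specify in SAP 8.1.2 a sensitivity analysis of the primary log-rank, Cox and Kaplan-Meier analyses in which COVID-19-related discontinuations without clearance are censored at planned Day 43 as worst outcome. Report it beside last-visit censoring, with the number of such exits by arm. Do not describe worst outcome as the protocol's explicit rule for these patients.

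The cost is a short blinded classification and one extra analysis. If worst outcome were made primary instead, power would fall by about 7 to 16 points at 5% to 10% leaving per arm, in a trial planned at 74%, and false positives could rise when exits are unequal.
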